## 1. INTRODUCTION / SYNOPSIS

Oral mucositis (OM) is an extremely common and often therapy limiting toxicity in patients receiving radiation therapy (RT) for head and neck cancer (HNC) (1). The pathobiology of OM is complex and some evidence suggests that changes within the oral microbiome during RT may play a contributing role (2). Chlorine dioxide is a known broad spectrum antiseptic against bacterial, fungal, and viral pathogens, and has been shown effective in the treatment of drinking water (3). Stabilized chlorine dioxide based rinsing products are now commercially available (CloSYS®) for the treatment of halitosis and oral hygiene use (4). It is believed that regulating the oral microbiome during RT could perhaps mitigate the incidence, onset, and duration of OM (5). No studies to date have evaluated the role of chlorine dioxide based oral rinses in preventing and treating OM associated with RT for HNC patients.

### 1.1 Phase

This is a Phase II, single center, prospective, randomized, double-blind, placebo-controlled study assessing the effects of stabilized chlorine dioxide oral rinse versus placebo on incidence, time to onset, duration, and patient reported outcomes on radiation therapy related OM, RT interruption, and changes in oral microbiome and cytokine composition.

### 1.2 Indication

Stabilized chlorine dioxide oral rinse for the treatment of RT related OM.

### 1.3 Endpoints

Primary:

- To evaluate and compare CloSYS® Unflavored Oral Rinse effect on the incidence of severe OM as measured by the World Health Organization (WHO) scale ( $\geq$ WHO Grade 3)

Grade	Description
0 (none)	None
I (mild)	Oral soreness, erythema
II (moderate)	Oral erythema, ulcers, solid diet tolerated
III (severe)	Oral ulcers, liquid diet only
IV (life-threatening)	Oral alimentation impossible

References:

WHO: <http://www.who.int/en/>

Secondary:

- To evaluate and compare ClōSYS® Unflavored Oral Rinse effect on the time to onset of severe OM ( $\geq$ WHO Grade 3)
- To evaluate and compare ClōSYS® Unflavored Oral Rinse effect on the duration of severe OM ( $\geq$ WHO Grade 3)
- To evaluate and compare ClōSYS® Unflavored Oral Rinse effect in patient reported outcomes as measured by the Oral Mucositis Weekly Questionnaire (OMWQ) (6) and Patient Reported Outcomes version of the Common Terminology Criteria for Adverse Events (PRO-CTCAE)
- To evaluate and compare ClōSYS® Unflavored Oral Rinse effect on rates of RT interruption

Exploratory:

- To evaluate and compare ClōSYS® Unflavored Oral Rinse effect on the oral microbiome
- To evaluate and compare ClōSYS® Unflavored Oral Rinse effect on salivary TNF $\alpha$ , IL-1 $\beta$ , and IL-6 levels

## 1.4 Patient Population

Eligible subjects must be able to understand and sign the study specific subject consent form. They must be  $\geq$ 18 years of age, have a Karnofsky Performance Status Scale (KPS) of  $\geq$ 60 with confirmed histologic or cytologic diagnosis of HNC (stage I-IV) for which they are receiving definitive or post-operative treatment with either RT alone or in combination with systemic therapy. Subjects may not have previous allergies to chlorine dioxide products and must fulfill the inclusion and exclusion criteria found in Section 6. Approximately 24 subjects will be randomized in a 1:1 ratio to stabilized chlorine dioxide rinse and placebo rinse. Twenty evaluable subjects (10 in each group) are needed in this pilot study to meet 81% statistical power (assuming a one-sided alpha of 0.05). We plan to recruit an additional 4 subjects to account for a 20% drop out/study non-compliance rate to ensure we have 20 evaluable subjects.

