## 2.3 Number of subjects

[figure not shown]
Approximately 24 will be recruited for this pilot study. Twenty evaluable subjects are needed to meet 81% statistical power (assuming a one-sided alpha of 0.05). We plan to recruit 4 additional subjects to account for a 20% drop out/study non-compliance rate.

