## **8.3 IP treatment/intervention/devise delays**

Subjects will begin oral rinsing the morning of day 1 of RT. The IP will be used twice per day continuously to the evening prior to their 1-month post-RT follow-up visit. If RT interruptions occur while taking the IP, subjects should continue IP per protocol, and additional IP may need to be given to the patient to complete the

schedule of treatment. All subjects will take a full continuous course of IP unless instructed by the PI to discontinue because of unacceptable toxicity as deemed appropriate by the PI. Subjects will be advised to rinse with the IP (preferably following meals) at 8 am ± 3 hours and 8 pm ± 3 hours.

If a subject misses a scheduled dose of IP within the recommended window, they should skip the missed dose and resume treatment at the next scheduled time. Treatment course will not be extended beyond the 1-month post-RT follow-up to compensate for missed doses. Subjects will stop treatment on the evening prior to their 1-month post-RT follow-up appointment with their Radiation Oncologist and return any remaining unused IP as described in Section 5.

If more than 7 consecutive days are missed of rinsing with the IP, the patient will be taken off study.

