#### **8.4 Definition of a Dose Limiting Toxicity (DLT)**

Subjects will continue on IP twice daily from day 1 of RT to the evening prior to their 1-month post-RT follow-up appointment with their Radiation Oncologist or unless instructed to stop IP as described elsewhere. If the subject meets the criteria listed above to be taken off the study, they will discontinue IP, but all assessments will continue to be collected. There are no known pre-specified DLTs associated with the IP.

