#### **9.6 Early Treatment Termination**

Subjects that terminate IP treatment prior to completing the planned treatment portion of the protocol will still be seen as per the study schedule and have an early termination visit at their 1-month post-RT follow-up appointment with their Radiation Oncologist. However, if the subject decides to withdraw from the study, no further information will be collected.

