### **15. REMOVAL OF SUBJECTS**

Subjects have the right to withdraw from the study at any time and for any reason without prejudice to their future medical care by the physician or at the institution. If this occurs, the investigator, or designee, is to discuss with the subject the safe and appropriate processes for discontinuation from the investigational product, intervention or device.

Subjects that wish to discontinue active IP treatment/intervention/device may elect to continue with the other protocol required assessments. The investigator should discuss with the subject the options for continuation of the study schedule of assessments (i.e. blood work, scans, physical exams, diaries) and collection of data, including endpoints and adverse events.

The investigator or designee must document the change in status of the subject's participation in the study and as applicable, the level of follow up that is agreed to

by the subject (i.e. agrees to follow up exams, adverse event review, phone contact, but not to further treatment and/or procedures).

Subject withdrawal of consent for a study indicates that the subject does not wish to receive further protocol required therapies or procedures, and the subject does not wish to, or is unable to continue further study participation. Subject data only up to the time when consent is withdrawn will be included in the analysis of the study.

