## **16. STATISTICAL CONSIDERATIONS**

The primary statistical analysis will compare the proportion of patients who develop severe OM ( $\geq$ WHO Grade 3) in patients randomized to ClōSYS Oral Rinse versus placebo. Analysis will be performed by estimating the proportion with exact 95% binomial confidence interval for each group separately. Statistical testing will use a chi-square test. As an alternative, Fisher's Exact Test will be used if the minimum expected value is  $< 5$ .

The secondary statistical endpoint of time to onset of severe OM will be tabulated and the median week to onset will be computed for each group. Comparison will be performed using a Wilcoxon Rank Sum Test (as the values are unlikely to be normally distributed). Duration of severe OM (number of weeks) will be analyzed similarly. The proportion of patients in each group with RT interruption will be tabulated and compared using a chi-square test.

The longitudinal measurements of the OMWQ and PRO-CTCAE, microbiome components and pro-inflammatory cytokines will be compared between groups using a linear mixed-effects model to account for the correlation among the measurements within an individual.

To justify the proposed sample size, we assume that 9/10 (90%) of the placebo control patients will experience severe OM within the 6-week period. Ten patients per group will allow us to detect a decrease to 40% (4/10) in the patients randomized to ClōSYS® Unflavored Oral Rinse with 81% statistical power (assuming a one-sided alpha of 0.05).

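### Four extra subjects on a target of 20 cover a 16.7% loss, not the stated 20%: at 20% loss, 24 subjects leave 19.2 evaluable (minor)

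*Combined protocol and SAP*

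**What the plan says.** Section 1.4 gives a requirement of 20 evaluable subjects, 10 in each group, for 81% power at a one-sided alpha of 0.05, with approximately 24 to be randomised 1:1. It adds: "We plan to recruit an additional 4 subjects to account for a 20% drop out/study non-compliance rate to ensure we have 20 evaluable subjects". Section 2.3 repeats this: "We plan to recruit 4 additional subjects to account for a 20% drop out/study non-compliance rate". Neither section defines what makes a subject evaluable, or whether non-compliance means missed rinses or missed visits.

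Section 16 describes the primary comparison as the proportion with severe oral mucositis ("WHO Grade 3) in patients randomized to" the active rinse versus placebo). It attaches no compliance condition and names no analysis set. Its sizing paragraph assumes 90% severe mucositis on placebo and 40% on active, with ten patients per group.

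On subjects who stop the rinse, Section 8.4 says that "they will discontinue IP, but all assessments will continue to be collected". Section 9.6 says that those who end treatment early "will still be seen as per the study schedule". Section 15 says that subjects who stop the rinse "may elect to continue with the other protocol required assessments", and on withdrawal of consent: "Subject data only up to the time when consent is withdrawn will be included in the analysis of the study".

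**The concern.** A loss rate applies to the number enrolled, so the number to enrol is the target divided by one minus the rate. Adding 20% of the target to the target is a common slip and always falls short. Here the sizing text promises a number of evaluable subjects that its own loss rate does not deliver.

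A second, smaller matter sits in the same sentence. If a non-compliant subject is still graded for mucositis, the primary outcome is known and nothing is lost to a comparison by assigned arm. Counting that subject as a loss leaves the reader unsure whether the primary denominator is about 24 patients or about 20 compliant ones. Section 4.2 hopes the results will inform a phase III trial, so the denominator should be plain.

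**Working it through.** **Inputs.** From Section 1.4: target 20 evaluable (10 per group), 4 added, about 24 in total, loss rate 20%. From Section 16: severe mucositis 90% on placebo and 40% on active, one-sided alpha 0.05.

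**The plan's figure.** 20 x (1 + 0.20) = 24. This reproduces the 24 exactly.

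**The figure that a 20% loss requires.** 20 / (1 - 0.20) = 25. If the two arms are to be equal, 10 / 0.80 = 12.5 per arm, so 13 per arm or 26 in all.

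**What 24 delivers.** 24 x 0.80 = 19.2 expected evaluable. The largest loss that still leaves 20 is 4 / 24 = 16.7%.

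**Chance of reaching the promised number.** This assumes that each subject is lost independently with probability 0.20, which the documents do not state.
- At least 20 of 24 evaluable: 46%.
- At least 10 of 12 in both arms: 0.558 x 0.558 = 31%.
- At least 20 of 25 evaluable: 62%.

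So even the correct division gives an expected number and does not ensure it.

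**Effect on power.** Pooled normal approximation, one-sided 0.05, with n per arm and mean rate 0.65:

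power = Phi[(0.50 - 1.645 x sqrt(2 x 0.65 x 0.35 / n)) / sqrt((0.90 x 0.10 + 0.40 x 0.60) / n)]

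- n = 10: (0.50 - 0.351) / 0.182 = 0.82, power 79.4%.
- n = 9.6 (19.2 in all): (0.50 - 0.358) / 0.185 = 0.77, power 77.8%.
- n = 9.5 (19 in all): power 77.4%.

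The drop is 1.6 to 2.0 points. The stated 81% is reproduced by the arcsine approximation at 10 per arm (81.0%), and the pooled formula is within 2 points of it.

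**Cost of analysing non-compliers.** Suppose 2 of 12 per arm are non-compliant and the 2 on active respond at the placebo rate (assumption). I enumerated all outcomes under Section 16's test rule: Fisher's exact test if the smallest expected count is below 5, otherwise chi-square without continuity correction, taken one-sided at 0.05.
- All 12 v 12, active arm made up of 10 patients at 40% and 2 at 90%: 66.1%.
- Compliant only, 10 v 10 at 90% v 40%: 67.1%.

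The difference is about 1 point. Both figures lie below 81% because the test rule usually selects Fisher's test at this size. That is a separate matter and not part of this point.

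**The case against.** The strongest reply is that this is one subject in a self-described pilot that says approximately 24, and that four on a target of twenty is literally 20% of the target. That stands as to weight. It does not rescue the statement that four extra subjects secure 20 evaluable at a 20% loss.

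The probabilities of 46% and 31% can also make a one-subject slip look large, since a correct 25 would reach 20 only 62% of the time. They are given only to show why the promise should go.

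A reader might infer more: that Section 16 contradicts Section 1.4, or that non-compliers will be excluded from the primary analysis. The documents do not support either reading. Section 16's wording names the arms and is not a formal analysis-set statement. A recruitment margin is not an exclusion rule, and no section orders exclusion. Non-compliance may also mean missed visits, which can cost an outcome, and Section 15 makes continued assessment elective for those who choose to stop the rinse.

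A reader might also take Section 8.3 ("If more than 7 consecutive days are missed of rinsing with the IP, the patient will be taken off study") to mean that these patients' outcomes are lost. Section 8.4 answers that: the rinse stops and assessments go on.

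**Conclusion.** The allowance in Sections 1.4 and 2.3 is wrong as written, and the error is minor. At the plan's own 20% loss, 24 subjects yield 19.2 evaluable and not 20; the margin covers 16.7%. The size is about one subject and roughly 2 points of power under the plan's assumed 90% and 40%. The arithmetic needs no assumption beyond the stated loss rate; the probabilities rest on independent losses.

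The undefined term evaluable and the unnamed analysis set are missing detail, not a contradiction. They justify a supporting clarification only. In the like-for-like comparison the choice of set changes power by about 1 point, on the assumption that non-compliant active patients respond like placebo.

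**What to change.** **Sections 1.4 and 2.3.** Either restate the allowance as 16.7% (4 of 24), or keep 20% and say that about 19 evaluable subjects are expected. Remove the word that promises 20. Enrolment stays at about 24.

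**Section 16, supporting clarification.** Add a sentence: the primary comparison includes all randomised patients with a known outcome, by assigned arm, regardless of rinse compliance. Define evaluable in Section 1.4 to match, and keep any compliant-only analysis as a sensitivity analysis.

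**Cost.** Wording in three sections, with no extra patients, visits or assessments and no change to how the rinse is given or stopped. The downside is possible dilution of the effect by non-compliers, about 1 point of power in the comparison shown above. No power gain is claimed.

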## 2. STUDY DESIGN

### 2.1 Phase

This is a Phase II, single center, prospective, randomized, double-blind, placebo-controlled study. Approximately 24 subjects will be randomized in a 1:1 ratio to stabilized chlorine dioxide oral rinse and placebo oral rinse.

### 2.2 Number of centers

One

This study will be performed by The University of Arizona Cancer Center Radiation Oncology Department at both the Banner University North Medical Campus Tucson (BUMC-N) and Orange Grove Clinic (OGC).

## 2.3 Number of subjects

[figure not shown]
Approximately 24 will be recruited for this pilot study. Twenty evaluable subjects are needed to meet 81% statistical power (assuming a one-sided alpha of 0.05). We plan to recruit 4 additional subjects to account for a 20% drop out/study non-compliance rate.

## 2.4 The subject participation time period

Subjects will be enrolled in the study for approximately 3 months, including screening time, treatment time, and follow-up at 30 days post RT.

Subjects enrolled in this study are undergoing treatment at BUMC-N or OGC as part of standard of care for the treatment of HNC. Study subjects will be treated with either stabilized chlorine dioxide oral rinse or placebo oral rinse twice daily during RT. Typical RT schedule is 6 to 7 weeks in length with treatments administered Monday through Friday. Subjects will begin the oral rinse (stabilized chlorine dioxide or placebo) on the morning of RT day 1. Whole unstimulated salivary collections, OM scoring, and validated OMWQ and PRO-CTCAE patient surveys will be completed at baseline (pre-RT), during weeks 2, 4, and 6 of RT during their planned on-treatment visits (OTVs), and at their 1-month post-RT follow-up appointment. The number of days and cause of RT treatment interruption will also be tracked.

## SCHEMA

### **3. OBJECTIVES**

#### **3.1 Primary Objective**

- To evaluate and compare ClōSYS® Unflavored Oral Rinse effect on the incidence of severe OM as measured by the World Health Organization (WHO) scale ( $\geq$ WHO Grade 3)

#### **3.2 Secondary Objectives**

- To evaluate and compare ClōSYS® Unflavored Oral Rinse effect on the time to onset of severe OM ( $\geq$ WHO Grade 3)
- To evaluate and compare ClōSYS® Unflavored Oral Rinse effect on the duration of severe OM ( $\geq$ WHO Grade 3)
- To evaluate and compare ClōSYS® Unflavored Oral Rinse effect in patient reported outcomes as measured by the Oral Mucositis Weekly Questionnaire (OMWQ) (6) and PRO-CTCAE
- To evaluate and compare ClōSYS® Unflavored Oral Rinse effect on rates of RT interruption
- To evaluate and compare ClōSYS® Unflavored Oral Rinse effect on the oral microbiome
- To evaluate and compare ClōSYS® Unflavored Oral Rinse effect on salivary TNF $\alpha$ , IL-1 $\beta$ , and IL-6 levels

### **4. BACKGROUND AND RATIONALE**

#### **4.1 Disease/Condition**

It is estimated that 61,760 new cases of head and neck cancer (HNC) will be diagnosed in the United States in 2016 (7). The majority of HNC patients receive radiation therapy (RT) as part of their care and nearly all are expected to develop treatment related oral mucositis (OM) (1). This often therapy limiting toxicity presents a challenge to practitioners and patients as it is known to reduce both quality of life and prognosis (8)(9). The pathobiology of OM is complex and involves alterations in mucosal barrier integrity, epithelial cell kinetics, extracellular matrix composition, vascular integrity, inflammatory mediators, and the oral microbiome (10)(11). In cases of high grade OM, infection and ulcerations may lead to a breach in the mucosal barrier, sepsis, and even death.

Few effective agents are available today for the prevention, delay, or reduction of RT related OM. Palifermin, a recombinant human keratinocyte growth factor, was demonstrated to improve the incidence, onset, and duration of high grade (WHO 3-4) OM in two independent phase III randomized clinical trials for patients receiving definitive and post-operative HNC RT, however both studies showed no impact on patient reported pain scores, RT compliance, or disease related outcomes (12)(13). Though FDA approved, the results of these studies have called into question the role of palifermin for OM, as it is a difficult drug to administer with weekly IV infusions during RT.

## **4.2 Investigational Product, Intervention, Device**

Chlorine dioxide is a known antimicrobial disinfectant which has been shown to be effective in the treatment of drinking water and is FDA approved for this indication among others (3). Clinically, chlorine dioxide has also been proven efficacious in the treatment of halitosis, which is thought to be related to its effect on decreasing the amount of volatile sulfur compounds and their associated bacterial organisms within the oral cavity (4). Commercially available products including ClōSYS® Unflavored Oral Rinse containing 0.1% (w/v) stabilized chlorine dioxide, are widely available for personal oral hygiene use.

Evidence exists that RT related OM is associated with a shift in the oral microbiome toward opportunistic species as resultant from alterations in salivary production and composition (2). It is believed that regulating the microbiome could eliminate, delay, or reduce the effects of OM as demonstrated by a meta-analysis of clinical trials evaluating various antimicrobials, none of which included chlorine dioxide based products (5). In addition to its broad spectrum antiseptic properties (bacterial, fungal, and viral), chlorine dioxide products are alcohol-free, sulfate-free, well-tolerated, available in rinse form, and possess anti-inflammatory properties which are critical to the prevention of OM (14).

We propose that the addition of twice daily usage of ClōSYS® Unflavored Oral Rinse to standard oral hygiene care during RT for HNC will decrease OM incidence, increase time to onset, decrease duration, and improve patient reported outcomes related to OM. Additionally, we hypothesize that ClōSYS® Unflavored Oral Rinse will reduce OM in patients receiving RT for HNC by mechanisms via changes in microbiome and inflammatory cytokine compositions. Lastly, we believe that decreased OM will potentially lead to less RT interruption. We hope that the results of this study will provide preliminary data for future phase III clinical trial testing.

## **4.3 Preclinical Experience**

The safety of chlorine dioxide and its metabolites (chlorite and chlorate) have been studied in animals extensively. Initial evaluations of high dose chlorine dioxide based products have shown adverse hematological, thyroid, and reproductive effects. In a review by Lyman Condie, these animal studies are highlighted in monkey, rat, and mouse experiments, which have shown that at high doses of exposure (>10mg/L or >10mg/kg/d) changes in several key physiologic endpoints have been clearly documented (15). Some studies have shown that chlorine dioxide and its metabolites (chlorite and chlorate) can cause oxidation of hemoglobin into methemoglobin and a subsequent reduction in red cell count by virtue of hemolytic anemia. Other studies have shown decreases in rat T4 levels leading to functional hypothyroidism. Further studies have shown sperm head abnormalities in mice exposed to high levels of chlorine dioxide for 5 days. To our knowledge, no animal studies have specifically evaluated chlorine dioxide in its potential protective effects on OM.

